### 3.0 STUDY DESIGN

**3.1 Study design:** This is a Phase 2 randomized two arm trial of nivolumab alone or in combination with THU-Dec, in previously treated patients with stage IV Non-Small Cell Lung Cancer (NSCLC). The primary goal of this trial is to compare the efficacy of oral THU-Dec as a way of enhancing the anti-tumor immune response to nivolumab to that of nivolumab alone. The primary efficacy endpoint is overall RECIST v1.1-defined response. To accomplish this goal 60 patients will be randomized 2:1 to THU-Dec plus nivolumab or nivolumab only respectively.

**3.2 Statistics and Sample size justification:** The primary goal of this trial is to compare the efficacy of immune priming with oral tetrahydrouridine (THU) plus decitabine (THU-Dec) and immune check-point inhibitor nivolumab (THU-Dec+nivolumab) to that of nivolumab alone. The primary efficacy endpoint is overall response. To accomplish this goal 60 patients will be randomized 2:1 to THU-Dec+nivolumab versus nivolumab alone (standard of care) respectively. The purpose of the nivolumab alone arm is to support the notion that the population studied is typical of the general population for which nivolumab has an established response rate of 20%. If the THU-Dec+nivolumab arm has a response rate of 35% or higher, we will consider it worthy of further investigation in a phase III trial. Thus, using a two-stage design (<http://www.swogstat.org/stat/public/twostage.htm>), with  $\alpha = 0.1$  and  $\beta = 0.2$ , we compute that 20 patients will be needed in each of two stages in the THU-Dec+nivolumab arm. If, after the 1st stage of 20 patients in the THU-Dec+nivolumab arm, 2 or fewer respond, the trial will be stopped and the null hypothesis that THU-Dec+nivolumab is no better than nivolumab will be accepted, else the trial continues for an additional 20 patients, at the end of which if 13 or more respond of the 40

patients in the THU-Dec+nivolumab arm, the null hypothesis is rejected and experimental arm of THU-Dec+nivolumab is recommended for further study.

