As an additional exploratory analysis we will compare response rates between treatment groups. We expect a 20% response rate in our control arm of 20 patients. The 95% confidence interval of the proportion  $4/20$  is 7% to 44%. It thus includes our treatment arm expected response rate of 35%. It is therefore very unlikely that our control arm will disprove our assumption that our sample population has a historical response rate of 20%. Thus, to increase the likelihood of gaining some information from our control arm, differences in proportions will be compared between arms. Using a calculator for [two arm binomial studies](#) we compute that the power to detect a difference in rates between our control arm and our treatment arm of 40 patients, assuming one-sided tests,  $\alpha=0.10$  and holding the treatment arm response rate at 35%, is, respectively, 89%, 70%, 50%, 32% and 18% for control response rates of 5%, 10%, 15%, 20%, and 25%. Thus, if our control arm rates are  $<15\%$ , we have  $>50\%$  chance of detecting a difference in response. In addition, we will evaluate the PD-L1 expression in both the control and treatment arm after every 20 patients. If there is  $>10\%$  difference in the PD-L1 status between the groups, we will stratify randomization by PD-L1 status for additional patients to balance the PD-L1 status.

Secondary endpoints include progression-free survival (progression is defined as progression by both RECIST v1.1), overall survival, and toxicity. Progression-free and overall survival will be summarized using the Kaplan-Meier method. Adverse events will be graded using CTCAE version 4.0 criteria, categorized by organ system, and summarized using frequency counts and percentages. With 20 patients treated with nivolumab only and 40 with THU-Dec+nivolumab the probability of observing at least one toxicity of a particular type and/or grade on each arm is 64% and 87%, respectively, if the risk of such an event is 5%, i.e.  $0.64 = (1-0.95^{20})$ .

Methods such as Fisher's exact test, chi-square tests, logistic regression (categorical data), the log-rank test and proportional hazards models (time to event data) will be used to compare patient groups. These analyses are primarily exploratory and it is acknowledged that they will have relatively low statistical power.

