### **3.3 Replacement of Subjects**

- If a subject is withdrawn from the study before week 8 for reasons not related to toxicity of study drug, the subject will be replaced.
- If a subject does not take at least 12 of the intended 16 doses in the first 8 weeks, the subject will be replaced because he/she has not taken enough THU-Dec that analysis of the primary end-point will be meaningful.

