## 12.0 MEASUREMENT OF EFFECT

### 12.1 Primary End Point

***Objective response:*** Objective response (OR) is the primary endpoint of this trial, subjects with measurable disease will be assessed by standard criteria. For the purposes of this study, subjects should be re-evaluated with CT scan with contrast (if clinically indicated

non-contrast CT or PET/CT could be used in lieu of CT with contrast) every 8 of weeks i.e after every 2 cycles (4 treatments) of Nivolumab.

Evaluation of response: Response and progression will be evaluated in this study using the Response Evaluation Criteria in Solid Tumors (RECIST) guideline (version 1.1). For the purpose of this study treatment will be discontinued in patients who experience disease progression by RECIST v1.1 (see Appendix IVa) with the following caveat: since it is known that there can be initial progression by RECIST v1.1 criteria with immune checkpoint blockade followed by subsequent regression and clinical benefit, if the treating clinical team and the patient judge that they have benefitted from therapy, treatment continuation is allowed even if there is disease progression by RECIST v1.1 criteria. However, patients should have confirmed stable disease or better at the time of the following scheduled imaging time-point. **ORR is defined as** the proportion of all randomized subjects whose best overall response (BOR) from baseline is either a CR or PR per RECIST v1.1 criteria. BOR is determined by the best response designation recorded between the date of randomization and the date of objectively documented progression or the date of subsequent anti-cancer therapy, whichever occurs first. For subjects without documented progression or subsequent anticancer therapy, all available response designations will contribute to the BOR determination. For subjects who continue treatment beyond progression, the BOR should be determined based on response designations recorded at the time of the initial RECIST v1.1.

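### Section 3.2 states beta = 0.2 for 20% versus 35%, but the two-stage rule it specifies has exact power 0.685, so a true 35% response rate is missed 31.5% of the time.

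*Combined protocol and SAP*

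**What the plan says.** Section 3.2 (Statistics and Sample size justification) bases the primary decision on the experimental arm alone. The null value is the nivolumab rate: "nivolumab has an established response rate of 20" per cent. The target is set by the statement that if the combination arm "has a response rate of 35% or higher, we will consider it worthy of further investigation in a phase III trial".

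From these rates, with alpha = 0.1 and beta = 0.2, the section reports the stage sizes: "we compute that 20 patients will be needed in each of two stages in the THU-Dec+nivolumab arm". The stage 1 rule is that if, among the first 20, "2 or fewer respond, the trial will be stopped and the null hypothesis" is accepted. Otherwise 20 more patients are added, and the null is rejected "at the end of which if 13 or more respond of the 40" patients.

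The next part of 3.2, on the control arm's confidence interval, treats 35% as the rate expected in the treatment arm: "It thus includes our treatment arm expected response rate of 35" per cent. Section 6.5 (Stopping Rule) repeats the stage 1 boundary but not the final cut-off. Attained error rates for the rule are not given anywhere.

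**The concern.** The stated beta and the stated cut-off belong to one design, so they should agree. If the final cut-off is too high for the stated beta, the trial's go/no-go decision has less power than a reader of 3.2 would conclude.

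This matters most when a negative result is interpreted. A final count of 12 of 40 (30%) would count as failure in a trial described as having 80% power at 35%. The comparison between arms offers little protection: 3.2 labels it exploratory and gives it 32% power when the control rate is 20% and the treatment rate 35%.

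**Working it through.** **Inputs, all from section 3.2.** Null rate 0.20; target rate 0.35; alpha 0.10; beta 0.20 (power 0.80); 20 patients per stage; continue if at least 3 of 20 respond; reject if at least 13 of 40 respond in total. The rule rejects in one direction only.

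**Formula.** With X1 the stage 1 responders and X2 the stage 2 responders, both Binomial(20, p), the probability of rejecting is

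P(reject | p) = Σ over x = 3 to 20 of P(X1 = x) × P(X2 ≥ 13 − x).

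Evaluated at p = 0.20 this is the type I error; at p = 0.35 it is the power.

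**Can the stated beta be reproduced?** No. For the rule as written (final cut-off 13):

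| True rate | P(reject) |
|---|---|
| 20% | 0.0432 (alpha) |
| 35% | 0.6851 (power) |
| 37.5% | 0.7909 |
| 40% | 0.8711 |

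Power equals 0.80 at a true rate of about 37.7%. The miss rate at 35% is 1 − 0.6851 = 0.3149, and the shortfall is 0.80 − 0.685 = 0.115.

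**Where the loss arises.** The chance of stopping at stage 1 (2 or fewer of 20) is 0.206 at a true rate of 20% and 0.012 at 35%. At 35%, therefore, 0.315 − 0.012 = 0.303 of the miss probability comes from trials that continue and finish below 13. With no interim look, 13 of 40 has power 0.6857, almost the same.

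**Other readings of the 13-of-40 cut-off.** A normal approximation gives power 0.630 without and 0.690 with continuity correction. Stage 1 boundaries of 1, 3 or 4 give 0.6856, 0.6812 and 0.6636. None is near 0.80.

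**Neighbouring final cut-offs, same stage 1 rule.**

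| Reject at | Alpha (20%) | Power (35%) |
|---|---|---|
| 11 of 40 | 0.1592 | 0.8759 |
| 12 of 40 | 0.0871 | 0.7934 |
| 13 of 40 | 0.0432 | 0.6851 |

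A cut-off of 11 breaks the alpha limit. A cut-off of 12 respects it and comes just short of 0.80. The step from 12 to 13 costs 0.7934 − 0.6851 = 0.108 of power, nearly the whole shortfall.

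**Sample size.** Forty patients fit the stated targets: the one-sample normal formula with one-sided alpha 0.10 gives n = 38, and power 0.820 at n = 40. It is the cut-off that does not match.

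**If the number analysed is not 40.** Holding 20 in stage 1 and the final bar at 13, alpha and power are 0.029 and 0.601 for N = 38, 0.062 and 0.758 for N = 42, and 0.085 and 0.818 for N = 44. These figures place every added or lost patient in stage 2 and give all patients the same response probability.

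**The case against.** The strongest reply is that alpha and beta are calculator inputs attached to the stage sizes, that no sentence says the rule attains 80% power, and that 40 patients do fit those inputs. This does not hold up. The cut-offs are presented as part of the same design, directly after the error rates, and 35% is the only target rate given.

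A second reply is that the error is conservative. The rule is clear, can be carried out as written and keeps type I error below 0.10, so it cannot inflate a claim of efficacy. That is true, but it protects only against a false go. The false-negative risk is the one that 3.2 understates.

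A third point stands in part. Because 12 nearly reproduces the stated alpha and beta, 13 may be a slip, such as a confusion of more than with at least. The output of the cited online calculator is not in the documents, so the origin of 13 cannot be settled from them, and the authors should check it.

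A caution about the sensitivity figures also stands. Section 3.3 replaces patients with too little treatment ("the subject will be replaced because he/she has not taken enough THU-Dec"), while 12.1 defines the response rate as "the proportion of all randomized subjects whose best overall response (BOR) from baseline is either a CR or PR". If replaced patients remain in the denominator, they may well respond less often than 35%. The 0.818 at N = 44 is then optimistic and should not be read as showing that replacement cures the shortfall.

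**Conclusion.** The concern holds. For the rule as written, power at a true rate of 35% is 0.685 rather than 0.80, and the false-negative risk is 31.5%, more than one and a half times the stated 20%. Attained alpha of 0.043 complies with the 0.10 limit and is not an error in itself. The shortfall comes from the final cut-off, not from the sample size or the interim look.

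The result is exact. It rests on binomial responses with a common rate and on exactly 40 analysed patients in the experimental arm, 20 per stage, as 3.2 specifies. Because it misstates an operating characteristic of the primary decision, it must be corrected.

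**What to change.** **Default.** Keep 13 of 40 and state in 3.2 that the rule has exact alpha 0.043 and power 0.69 at a true rate of 35%, with 80% power at about 37.7%, in place of the present beta. State also that these figures assume exactly 40 analysed patients in the experimental arm. This costs a sentence or two, with no added patients and no change to the decision rule. The drawback is that the stated power looks less favourable.

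**Alternative.** Set the final cut-off at 12 or more of 40 and give its exact alpha (0.087) and power (0.793), noting that power is still just under 0.80. The false-go rate rises from 4.3% to 8.7%, within the stated 10%. Because this loosens the primary criterion, it is acceptable only if made and documented without reference to any accrued response data; the documents do not give accrual status. Checking the calculator output behind the 13 would help the authors choose, but does not remove this condition.

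Under either option, the stage 1 rule in 3.2 and 6.5 stays as written.

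### Does the exploratory between-arm response comparison need one named test before the arms are compared?

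*Combined protocol and SAP*

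**What the plan says.** Section 3.2 (Statistics and Sample size justification) sets the formal decision on the experimental arm alone. After the second stage the null hypothesis is rejected "at the end of which if 13 or more respond of the 40" patients.

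The between-arm comparison comes afterwards: "As an additional exploratory analysis we will compare response rates between treatment groups". Its inputs are given: "We expect a 20% response rate in our control arm of 20 patients", "our treatment arm of 40 patients", one-sided tests, alpha 0.10 and a treatment rate of 35%. The power row is "89%, 70%, 50%, 32% and 18% for control response rates of 5%, 10%, 15%, 20%, and 25" percent, credited to an online calculator for "two arm binomial studies". The section concludes that control rates below 15% leave a better than even chance of detecting a difference.

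The methods sentence later in the section is an open list, Fisher's "exact test, chi-square tests, logistic regression (categorical data"), followed by time-to-event methods. None is tied to the response comparison. The paragraph closes: "These analyses are primarily exploratory and it is acknowledged that they will have relatively low statistical power".

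**The concern.** With 40 and 20 patients, Fisher's test is conservative and the uncorrected chi-square runs close to its nominal level, so the same table can be significant by one and not by the other. The plan fixes sidedness and alpha but not the test, so the exploratory verdict could turn on a choice made after the responses are known. The printed power row names no test either, so it does not settle the choice. At stake is how the trial's only randomised comparison of the primary endpoint is reported.

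**Working it through.** **Inputs (all Section 3.2).** Treatment n = 40, control n = 20, treatment rate 35%, control rates 5 to 25%, one-sided alpha 0.10.

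**1. The plan's own figure, 32% at 35% versus 20%.** Pooled rate = (40 × 0.35 + 20 × 0.20)/60 = 0.30.
- Null SE = √[0.30 × 0.70 × (1/40 + 1/20)] = 0.1255.
- Alternative SE = √[0.35 × 0.65/40 + 0.20 × 0.80/20] = 0.1170.
- Continuity correction = 0.5 × (1/40 + 1/20) = 0.0375.
- Power = Φ[(0.15 − 0.0375 − 1.2816 × 0.1255)/0.1170] = Φ(−0.41) = 34.0%.

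Three normal approximations can be set against the printed row:

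| Approximation | 5% | 10% | 15% | 20% | 25% |
|---|---|---|---|---|---|
| Printed | 89 | 70 | 50 | 32 | 18 |
| Corrected as above, one-sided 0.10 | 89.1 | 71.5 | 51.6 | 34.0 | 20.6 |
| Corrected by shrinking control n to 20 − (r+1)/(rd), where r = 2 and d is the rate difference | 88.5 | 70.4 | 50.0 | 32.0 | 17.8 |
| Uncorrected, two-sided 0.10 | 87.9 | 69.3 | 48.9 | 31.5 | 18.6 |

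The row is reproducible, so it is not a mistake. More than one formula comes close, so the calculator's method cannot be inferred from the row.

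**2. Exact power of the listed methods.** Sum Bin(a; 40, 0.35) × Bin(b; 20, control rate) over all 41 × 21 tables that the test rejects at one-sided 0.10.

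| Test | 5% | 10% | 15% | 20% | 25% | Size at common 20% |
|---|---|---|---|---|---|---|
| Fisher, or corrected chi-square (same rejection region) | 91 | 74 | 53 | 35 | 21 | 4.9% |
| Uncorrected chi-square | 96 | 83 | 66 | 47 | 31 | 10.0% |
| Logistic, likelihood ratio | 96 | 85 | 68 | 50 | 33 | 10.9% |
| Logistic, Wald (0 or all responders in an arm counted as no rejection) | 60 | 71 | 62 | 46 | 31 | 8.0% |

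The likelihood-ratio row should not be read as a gain. Its size is 14.0% at a common rate of 10% and 21.7% at 5%, above the stated 0.10. Of the other rows, the uncorrected chi-square peaks at 10.6% over common rates of 5 to 50%. The fair spread at 35% versus 20% is therefore about 35% to 47%, and part of that is Fisher using only half of its nominal alpha.

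**3. How often the choice matters.** Every table rejected by Fisher is also rejected by the uncorrected chi-square, so disagreement is the difference in rejection probability: 47.5 − 35.0 = 12.5% of trials at 35% versus 20%, and 10.0 − 4.9 = 5.1% when both rates are 20%.

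**4. A concrete table, 13/40 versus 3/20.** Pooled rate 16/60 = 0.267; SE = √(0.267 × 0.733 × 0.075) = 0.121; z = (0.325 − 0.150)/0.121 = 1.445.
- One-sided p by uncorrected chi-square: 0.074.
- One-sided p by Fisher: 0.127.
- Decision rule: 13 of 40 meets the threshold, so the combination is recommended for further study under either p-value.

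**5. The plan's summary statement.** At a control rate of 15%, exact power is 53% (Fisher) and 66% (uncorrected chi-square), so the better-than-even claim below 15% holds for both. It fails for a Wald logistic test at very low control rates (44% at 3%, 32% at 2%), because a control arm with no responders gives no usable Wald statistic. That is the setting in which an analyst would turn to the exact test already on the list.

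**The case for a change.** The best argument for acting is that Section 3.1 makes comparison with nivolumab alone the trial's primary goal, and this is the only place where the randomised arms are compared on the primary endpoint. Section 3.2 adds the comparison in order to learn something from the control arm. Sidedness and alpha were fixed in advance, so leaving the test open leaves one choice that can flip the result. Among trials that meet the 13-of-40 rule at 35% versus 20%, Fisher and the uncorrected chi-square disagree in about 15%. Naming a test would take one sentence.

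The facts in that argument stand: no test is assigned, and the spread in power is real. Acknowledging low power does not by itself remove a choice made after seeing the data. What does not stand is that the plan is defective without the sentence. The result is labelled exploratory, no recommendation depends on it, and a table on which the tests split is weak evidence by either one. Nor is there a clearly better test to impose. Boschloo's exact test keeps its size within 9.8%, but its power is 46% against 47% for the uncorrected chi-square that the plan already lists. Choosing between conditional and unconditional tests is a matter on which statisticians differ.

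**Conclusion.** No change is needed. The plan leaves out a detail of an exploratory analysis, and the omission moves exact power between about 35% and 47% at 35% versus 20%. Any of the Fisher or chi-square tests, run at the stated one-sided 0.10 and reported by name, gives a usable exploratory result. The go/no-go decision is the same whichever is used. The printed power row is 2 to 4 points below Fisher's exact power and further below the uncorrected chi-square, so it does not oversell the comparison under either. A team that names its test beforehand would be following good practice, but nothing in the trial's conclusions waits on it.

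This rests on full enrolment of 40 and 20 patients, the plan's assumed rates, and the comparison remaining exploratory. Counting a stage-one stop as non-rejection changes power at 35% versus 20% by at most 0.2 points. If the comparison were ever promoted to support a claim of efficacy, the test would have to be fixed first.

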**- Frequency of THU and Dec ingestion:**

- THU ~10 mg/kg is administered 60 minutes before oral decitabine ~0.2 mg/kg 2X/week on consecutive days if there is no  $\geq$  grade 3 treatment-related non-hematologic toxicity and the ANC is  $>0.5 \times 10^9/L$  (if ANC is  $<0.5 \times 10^9/L$ , treatment is held until recovery above this threshold then resumed with a dose reduction as per Table 1).

- G-CSF neutropenia prophylaxis is recommended 1X/week if the ANC is  $<1.5 \times 10^9/L$

**Clinical Monitoring:** History and examination, laboratory tests, and regular radiologic assessments. Patients will continue study treatment until disease progression by clinical and/or radiologic parameters (RECIST v1.1), or unacceptable toxicity. Efficacy will be determined by radiographic evaluation and other measures as described above. THU-Dec safety profile will be determined by incidence of treatment emergent adverse events captured from the first dose of THU. Each adverse event will be summarized by grade, causality, expected/unexpected based on the current knowledge. Further, adverse events will be summarized by body system and at the patient level (worst grade for specified adverse event).

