### **3.4 Expected Duration of Treatment and Subject Participation**

Treatment on protocol monitoring continues until (i) disease progression (defined by RECIST v1.1 with the following caveat: since it is known that there can be initial progression by RECIST v1.1 criteria with immune checkpoint blockade followed by subsequent regression and clinical benefit, if the treating clinical team and the patient judge that they have benefitted from therapy, treatment continuation is allowed even if there is disease progression by RECIST v1.1 criteria. However, patients should have confirmed stable disease or better at the time of the following scheduled imaging time-point. If there

is progression at this following re-staging, patients should be discontinued from therapy); (ii) toxicity as defined in Section 7.1; or (iii) withdrawal of consent up to a maximum of 24 months.

At the end of the protocol-specified period of active study therapy, the sponsor will not continue to supply study drug to subjects/investigators unless the sponsor chooses to extend the study, which may include continuation of nivolumab. The investigator should ensure that the subject receives appropriate standard of care, which may include continued treatment with nivolumab.

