#### Nonserious Adverse Event Collection and Reporting

The collection of nonserious AE information should begin at initiation of study drug. All nonserious adverse events (not only those deemed to be treatment-related) should be collected continuously during the treatment period and for a minimum of 30 days following the last dose of study treatment, unless they start other treatments for the cancer within that time, transition to hospice or expire within 30 days after treatment. AE evaluation can be done by chart review and/or telephone encounter.

Nonserious AEs should be followed to resolution or stabilization, or reported as SAEs if they become serious. Follow-up is also required for nonserious AEs that cause interruption

or discontinuation of study drug and for those present at the end of study treatment as appropriate.

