## 12.2 Secondary End Point

a) *Progression free survival:* It is defined as the time from randomization to the date of the first documented tumor progression (per RECIST v1.1) or death due to anycause. Subjects who die without a reported prior progression will be considered to have progressed on the date of their death. Subjects who did not progress or die will be censored on the date of their last evaluable tumor assessment. Subjects who did not have any on study tumor assessments and did not die will be censored on the date they were randomized. Subjects who started any subsequent anti-cancer therapy without a prior reported progression will be censored at the last evaluable tumor assessment prior to initiation of the subsequent anti-cancer therapy. Progression will be assessed every 6 weeks (from the first on-study radiographic assessment) until disease progression is noted.

b) *Overall survival:* It is defined as the time from randomization to the date of death. A subject who has not died will be censored at last known date alive. OS will be followed continuously while subjects are on the study drug and every 3 months via in-person or phone contact after subjects discontinue the study drug.

c) *Safety and tolerability:* Safety and tolerability objective will be measured by the incidence of adverse events, serious adverse events, deaths, and laboratory abnormalities. Adverse event assessments and laboratory tests are performed at baseline, and continuously throughout the study at the beginning of each subsequent cycle. The safety analysis will be performed in all treated subjects. Descriptive statistics of safety will be presented using

National Cancer Institute (NCI) Common Terminology Criteria for Adverse Events (CTCAE) version 4.0 by treatment arm. All treatment emergent AEs, drug-related AEs, SAEs and drug-related SAEs will be tabulated using worst grade per NCI CTCAE v 4.0 criteria by system organ class and preferred term. On-study lab parameters including hematology, coagulation, chemistry, liver function and renal function will be summarized using worst grade per NCI CTCAE v 4.0 criteria.

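### By-arm toxicity is summarized only by crude counts, percentages and worst grade, although each patient's AE observation time depends on how long treatment lasts

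*Combined protocol and SAP*

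**What the plan says.** Toxicity of the combination is a secondary objective (section 2.0) and a secondary endpoint (sections 3.2 and 12.2).

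- **Summary method.** Section 3.2: "Adverse events will be graded using CTCAE version 4.0 criteria, categorized by organ system, and summarized using frequency counts and percentages". Section 12.2(c): "All treatment emergent AEs, drug-related AEs, SAEs and drug-related SAEs will be tabulated using worst grade per NCI CTCAE v 4.0 criteria", with descriptive statistics under CTCAE "version 4.0 by treatment arm". The Protocol Summary describes the THU-Dec safety profile through the "incidence of treatment emergent adverse events captured from the first dose of THU".
- **Length of treatment.** Section 3.4 continues treatment to progression, toxicity or "withdrawal of consent up to a maximum of 24 months", which I read as a cap on treatment. It allows treatment past RECIST progression if benefit is judged.
- **AE collection.** Section 8.2.1 has nonserious AEs "collected continuously during the treatment period and for a minimum of 30 days following the last dose of study treatment", with earlier ends for new cancer treatment, hospice or death. Section 8.4 runs collection from Cycle 1 Day 1 to 30 days after the final dose.
- **Comparisons.** The tests and models listed in section 3.2 "will be used to compare patient groups". Toxicity is not named among their targets, and the analyses are called primarily exploratory, with low power.

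No section plans a fixed-window AE summary, a time-to-AE endpoint, a rate per unit of exposure, or a summary of treatment duration by arm.

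**The concern.** A crude percentage estimates the chance of an event during however long the patient was watched. Here that length is partly an outcome of treatment. The trial's hypothesis is that THU-Dec improves the efficacy of nivolumab; if so, combination patients may stay on treatment longer and accumulate more events at the same monthly rate. If THU-Dec is poorly tolerated and stopped early, the reverse can occur. Worst grade behaves the same way, being a maximum over the observed period.

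Section 3.2 uses Kaplan-Meier for progression-free and overall survival, so variable follow-up is handled for efficacy but not for toxicity. Tables printed side by side will be read as a comparison, whatever their formal status.

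**Working it through.** **1. The plan's own toxicity figure.** Section 3.2 gives the probability of at least one event at 5% risk. 1 - 0.95^20 = 0.6415 and 1 - 0.95^40 = 0.8715, matching the stated 64% and 87%. The calculation gives both arms the same risk, with no reference to exposure.

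**2. Inputs for the illustration.** From the protocol: 20 and 40 patients, the 24-month cap C, and the 30-day tail d (30/30.44 = 0.986 months). Assumed, because the protocol gives none: a constant AE hazard h, equal in both arms, of 0.05, 0.10 or 0.20 per month; exponential time on treatment with median m of 3.5 months (control) and 2.5, 5 or 7 months (THU-Dec).

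**3. Formula.** With λ = ln 2 / m,

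crude risk = 1 - e^(-hd) × [ λ/(λ+h) × (1 - e^(-(λ+h)C)) + e^(-(λ+h)C) ].

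Example, h = 0.10:
- m = 3.5: λ = 0.198, bracket 0.6647, e^(-hd) = 0.9061, risk 1 - 0.6023 = 39.8%.
- m = 7: λ = 0.0990, bracket 0.5018, risk 1 - 0.4547 = 54.5%.

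**4. Results** (difference from control in points, from unrounded risks):

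| h per month | Control, 3.5 mo | THU-Dec, 2.5 mo | THU-Dec, 5 mo | THU-Dec, 7 mo |
|---|---|---|---|---|
| 0.05 | 23.9% | 19.3% (-4.6) | 29.8% (+5.8) | 35.9% (+11.9) |
| 0.10 | 39.8% | 33.4% (-6.4) | 47.2% (+7.5) | 54.5% (+14.8) |
| 0.20 | 59.1% | 52.3% (-6.8) | 66.4% (+7.2) | 72.8% (+13.6) |

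Every difference arises at an identical event rate.

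**5. Rare events.** Set h so that the control risk is the plan's 5%, with an assumed control median of 3 months. The THU-Dec risk becomes 6.8% at 1.5 times the median and 8.4% at twice the median. The chance of at least one event among 40 rises from 87% to 94% or 97%.

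**6. Sampling noise.** For 39.8% versus 47.2%, SE = √(0.398×0.602/20 + 0.472×0.528/40) = 13.5 points, so +7.5 is about 0.6 SE. The largest artefact, +14.8, is about 1.1 SE.

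**7. Common window.** Simple incidence by week w is 1 - E[e^(-h·min(T+d, w))], where T is time on treatment. At h = 0.10 and medians of 3.5 versus 7 months:
- 8 weeks (1.84 months): 16.2% versus 16.5%.
- 16 weeks (3.68 months): 26.2% versus 28.3%. Censoring at the end of AE follow-up gives 1 - e^(-0.368) = 30.8% in both arms.

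**8. Early-onset events and exposure-adjusted rates.** Let the hazard be 0.2 per month for the first 2 months only, equal in both arms, with medians of 3.5 versus 7 months.
- Crude risk is 31.6% versus 32.3%, nearly unbiased.
- Expected events per patient are 0.2 × [d + (1 - e^(-λ(2-d)))/λ] = 0.381 versus 0.390.
- Mean observation is (1 - e^(-24λ))/λ + d = 5.99 versus 10.15 months.
- The rate is therefore 0.064 versus 0.038 per patient-month, a false reduction of about 40% in the longer-treated arm.

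**The case against.** The strongest reply is that nothing decisive rests on these tables. A reader might infer that toxicity, together with response rate, decides whether THU-Dec goes forward. The documents do not support that: section 3.2 recommends further study on 13 or more responders among 40 and on nothing else. Nor is the toxicity rule in section 6.5 exposed. It counts removals among the first 5 combination patients before cycle 2, in one arm over a short common period. A reader might also infer a biased formal test of toxicity between arms, but none is named; section 12.2(c) calls the output descriptive, and section 3.2 gives the control arm the purpose of checking that the population is typical. All of this stands.

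The size is also wholly assumed, the larger figures need THU-Dec to double time on treatment, and one comparison cannot separate the artefact from noise. That stands too. But the artefact is systematic across AE terms that recur over time, and a larger sample would not remove it.

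Finally, the proportion of treated patients with an event over treatment as given is a legitimate quantity, and extra toxicity from longer treatment is real harm. That is a reason to keep the crude tables, not to leave them as the only display. Replacing them with exposure-adjusted rates would be a mistake: step 8 shows that such rates can mislead more than the crude table when events come early.

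**Conclusion.** The gap is real and modest. The only planned by-arm toxicity summaries ignore an observation time that depends on disease control, tolerability and the judgement to treat past progression. Under the stated assumptions of constant equal hazards, exponential time on treatment, the 30-day tail and the 24-month cap, the artefact is about -5 to -7 points if THU-Dec shortens treatment and +6 to +15 if it lengthens it. It is under 4 points for a 5% event at twice the control median and close to zero for events confined to the first two months.

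Two stronger readings should be resisted. The combination will not necessarily look more toxic, since the direction depends on which arm stays on treatment longer. And time at risk does not simply end at progression; it ends about 30 days after treatment stops, with the exceptions in sections 3.4 and 8.2.1. No stated figure is wrong. What is missing is an analysis that would let the secondary toxicity objective be read separately from treatment duration.

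**What to change.** In sections 3.2 and 12.2(c), keep the crude and worst-grade tables and add:

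1. Treatment duration by arm.
2. As the main by-arm safety display, the cumulative incidence of AEs in a common window from the first dose of study treatment: the first 8 weeks and the first 16 weeks. These match the protocol's own staging times, and the 8-week window largely precedes the response-dependent THU-Dec dose increases that section 7.2 allows from week 8. Define the start for both arms, because control patients take no THU.
3. A stated rule for patients who leave within the window: death, and end of AE follow-up, each handled as censoring or as a competing event. The choice matters little at 8 weeks. At 16 weeks, treating end of follow-up as a competing event would leave the roughly 2-point gap in step 7, while censoring assumes that leaving is unrelated to AE risk.

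Exposure-adjusted rates may be added only as a supplement, with the caveat that they assume a roughly constant hazard and dilute early-onset events.

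The cost is a few more tables from dosing dates and AE onset dates (section 8.2.3 requires the latter), with no new patients or visits. The window display omits late events, which remain in the crude tables.
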